5.1.3 Lifestyle Restrictions

5.1.3.1 Meals and Dietary Restrictions

Participants should maintain a normal diet unless modifications are required to manage an AE such as diarrhea, nausea, or vomiting.

5.1.3.2 Contraception

Lenvatinib and pembrolizumab may have adverse effects on a fetus in utero. Refer to Appendix 3 for approved methods of contraception.

Based on its mechanism of action, lenvatinib can cause fetal harm when administered to a pregnant woman. Lenvatinib may also result in reduced fertility in females of reproductive potential and may result in damage to male reproductive tissues leading to reduced fertility of unknown duration. In animal reproduction studies, oral administration of lenvatinib during organogenesis at doses below the recommended human dose resulted in embryo toxicity and teratogenicity in rats and rabbits.

Participants should be informed that taking the study medication may involve unknown risks to the fetus (unborn baby) if pregnancy were to occur during the study. In order to participate in the study, participants of childbearing potential must adhere to the contraception requirement (Appendix 3) from the day of study medication initiation (or 14 days prior to the initiation of study medication for oral contraception) throughout the study period up to 120 days after the last dose of study medication. If there is any question that a participant of childbearing potential will not reliably comply with the requirements for contraception, that participant should not be entered into the study.

5.1.4 Pregnancy

If a participant inadvertently becomes pregnant while on treatment with lenvatinib or pembrolizumab, the participant will be immediately discontinued from study intervention.

5.1.5 Use in Nursing Women

It is unknown whether lenvatinib or pembrolizumab are excreted in human milk. Since many drugs are excreted in human milk, and because of the potential for serious adverse reactions in the nursing infant, participants who are breastfeeding are not eligible for enrollment.

5.2 Trial Treatments

The treatment to be used in this trial is outlined below in Table 2

Table 2 Trial Treatment

Drug	Dose/Potency	Dose Frequency	Route of Administration	Regimen/Treatment Period	Use
Pembrolizumab	200 mg	Q3W	IV infusion	Day 1 of each 3 week cycle	Experimental
Lenvatinib	20 mg	Daily	Oral	Day 1-21 of each 3 week cycle	Experimental

Trial treatment should begin on the day of allocation or as close as possible to the date on which treatment is allocated/assigned.

5.2.1 Timing of Dose Administration

Trial treatment should be administered on Day 1 of each cycle after all procedures/assessments have been completed as detailed on the Trial Flow Chart (Section 6.0). Trial treatment may be administered up to 3 days before or after the scheduled Day 1 of each cycle due to administrative reasons.

All trial treatments will be administered on an outpatient basis.

Pembrolizumab 200 mg will be administered as a 30-minute IV infusion every 3 weeks. Sites should make every effort to target infusion timing to be as close to 30 minutes as possible. However, given the variability of infusion pumps from site to site, a window of -5 minutes and +10 minutes is permitted (i.e., infusion time is 30 minutes: -5 min/+10 min).

The Pharmacy Manual contains specific instructions for the preparation of the pembrolizumab infusion fluid and administration of infusion solution.

Lenvatinib 20 mg will be provided for the patient to take orally once daily for 3 weeks. The patient will maintain a pill diary, and all pills will be counted to ensure proper home self-administration. The patient will be instructed to take lenvatinib every 24 hours, as close to the exact hour as possible. If a dose of lenvatinib is missed and cannot be taken within 12 hours from the scheduled administration, the participant should skip this dose and take the next dose at the scheduled time the next day.

5.2.2 Dose Modification and toxicity management

5.2.2.1 Dose Modification and toxicity management for immune-related AEs associated with pembrolizumab and combination therapy

AEs associated with pembrolizumab exposure, including coadministration with additional compounds, may represent an immunologic aetiology. These immune-related AEs (irAEs) may occur shortly after the first dose or several months after the last dose of pembrolizumab/combination treatment and may affect more than one body system simultaneously. Therefore, early recognition and initiation of treatment is critical to reduce complications. Based on existing clinical study data, most irAEs were reversible and could be managed with interruptions of pembrolizumab/combination treatment, administration of corticosteroids and/or other supportive care. For suspected irAEs, ensure adequate evaluation to confirm etiology or exclude other causes. Additional procedures or tests such as bronchoscopy, endoscopy, skin biopsy may be included as part of the evaluation. Dose modification and toxicity management guidelines for irAEs associated with pembrolizumab/combination treatment are provided in Table 3.

Attribution of Toxicity:

When study interventions are administered in combination, attribution of an adverse event to a single component is likely to be difficult. Therefore, while the investigator may attribute a toxicity event to the combination, to lenvatinib alone or to pembrolizumab alone, for adverse events listed in Table 3, both interventions must be held according to the criteria in Table 3: Dose Modification and Toxicity Management Guidelines for Immune-Related Adverse Events Associated with Pembrolizumab.

Holding Study Interventions:

When study interventions are administered in combination, if the AE is considered immune-related, both interventions should be held according to recommended dose modifications.

Restarting Study Interventions:

Participants may not have any dose modifications (no change in dose or schedule) of pembrolizumab in this study, as described in Table 3.

- If the toxicity does not resolve or the criteria for resuming treatment are not met, the participant must be discontinued from all study interventions.
- If the toxicities do resolve and conditions are aligned with what is defined in Table 3, the combination of lenvatinib and pembrolizumab may be restarted at the discretion of the investigator. In these cases where the toxicity is attributed to the combination or to lenvatinib alone, re-initiation of pembrolizumab as a monotherapy may be considered at the principal investigator's discretion .]

Table 3. Dose modification and toxicity management guidelines for immune-related AEs associated with pembrolizumab monotherapy and IO Combinations

General instructions:				

 1. Severe and life-threatening irAEs should be treated with IV corticosteroids followed by oral steroids. Other immunosuppressive treatment should begin if the irAEs are not controlled by corticosteroids. 2. Study intervention must be permanently discontinued if the irAE does not resolve or the corticosteroid dose is not ≤ 10 mg/day within 12 weeks of the last study intervention treatment. 3. The corticosteroid taper should begin when the irAE is \leq Grade 1 and continue at least 4 weeks. 4. If study intervention has been withheld, study intervention may resume after the irAE decreased to \leq Grade 1 after corticosteroid taper. 				

irAEs	Toxicity Grade (CTCAE v5.0)	Action With Pembrolizumab	Corticosteroid and/or Other Therapies	Monitoring and Follow-up
Pneumonitis	Grade 2	Withhold	
 • Administer corticosteroids (initial dose of 1 to 2 mg/kg prednisone or equivalent) followed by taper • Add prophylactic antibiotics for opportunistic infections 	
 • Monitor participants for signs and symptoms of pneumonitis • Evaluate participants with suspected pneumonitis with radiographic imaging and initiate corticosteroid treatment
	Recurrent Grade 2, Grade 3 or 4	Permanently discontinue		
Diarrhea/Colitis	Grade 2 or 3	Withhold	
 • Administer corticosteroids (initial dose of 1 to 2 mg/kg prednisone or equivalent) followed by taper 	
 • Monitor participants for signs and symptoms of enterocolitis (ie, diarrhea, abdominal pain, blood or mucus in stool with or without fever) and of bowel perforation (ie, peritoneal signs and ileus)

irAEs	Toxicity Grade (CTCAE v5.0)	Action With Pembrolizumab	Corticosteroid and/or Other Therapies	Monitoring and Follow-up
	Recurrent Grade 3 or Grade 4	Permanently discontinue		
 Participants with \geqGrade 2 diarrhea suspecting colitis should consider GI consultation and performing endoscopy to rule out colitis Participants with diarrhea/colitis should be advised to drink liberal quantities of clear fluids. If sufficient oral fluid intake is not feasible, fluid and electrolytes should be substituted via IV infusion
AST or ALT Elevation or Increased Bilirubin	Grade 2 ^a	Withhold	
 Administer corticosteroids (initial dose of 0.5 to 1 mg/kg prednisone or equivalent) followed by taper 	
 Monitor with liver function tests (consider weekly or more frequently until liver enzyme value returned to baseline or is stable)
	Grade 3 ^b	Withhold; discontinue only if not improving on steroids within 7 days	
 Administer corticosteroids (initial dose of 1 to 2 mg/kg prednisone or equivalent) followed by taper 	
	Grade 4 ^c	Permanently discontinue	Administer corticosteroids (initial dose of 1 to 2 mg/kg prednisone or equivalent) followed by taper	
T1DM or Hyperglycemia	New onset T1DM or Grade 3 or 4 hyperglycemia	Withhold ^d	
 Initiate insulin replacement therapy for participants with T1DM 	
 Monitor participants for hyperglycemia or other signs and symptoms of diabetes

irAEs	Toxicity Grade (CTCAE v5.0)	Action With Pembrolizumab	Corticosteroid and/or Other Therapies	Monitoring and Follow-up
	associated with evidence of β -cell failure		
 Administer antihyperglycemic in participants with hyperglycemia 	
Hypophysitis	Grade 2-3	Continue unless clinically unstable	
 Administer corticosteroids and initiate hormonal replacements as clinically indicated 	
 Monitor for signs and symptoms of hypophysitis (including hypopituitarism and adrenal insufficiency)
	Grade 4	Withhold	
 The decision to withhold or permanently discontinue pembrolizumab is at the discretion of the investigator or treating physician. If control achieved or \leq Grade 2, pembrolizumab may be resumed. 	
Hyperthyroidism	Grade 2	Continue	
 Treat with nonselective beta-blockers (eg, propranolol) or thionamides as appropriate 	
 Monitor for signs and symptoms of thyroid disorders
	Grade 3 or 4	Withhold	
 The decision to withhold or permanently discontinue pembrolizumab is at the discretion of the investigator or treating physician. If control achieved or \leq Grade 2, pembrolizumab may be resumed. 	

irAEs	Toxicity Grade (CTCAE v5.0)	Action With Pembrolizumab	Corticosteroid and/or Other Therapies	Monitoring and Follow-up
Hypothyroidism	Grade 2, 3 or 4	Continue	
 Initiate thyroid replacement hormones (eg, levothyroxine or liothyronine) per standard of care 	
 Monitor for signs and symptoms of thyroid disorders
Nephritis: grading according to increased creatinine or acute kidney injury	Grade 2-3	Withhold	
 Administer corticosteroids (prednisone 1 to 2 mg/kg or equivalent) followed by taper 	
 Monitor changes of renal function
	Grade 4	Permanently discontinue		
Neurological Toxicities	Grade 2	Withhold	
 Based on severity of AE administer corticosteroids 	
 Ensure adequate evaluation to confirm etiology and/or exclude other causes
	Grade 3 or 4	Permanently discontinue		
Myocarditis	Grade 2	Withhold	
 Based on severity of AE administer corticosteroids 	
 Ensure adequate evaluation to confirm etiology and/or exclude other causes
	Grade 3 or 4	Permanently discontinue		
Exfoliative Dermatologic Conditions	Suspected SJS, TEN, or DRESS	Withhold	
 Based on severity of AE administer corticosteroids 	
 Ensure adequate evaluation to confirm etiology or exclude other causes
	Confirmed SJS, TEN, or DRESS	Permanently discontinue		
All Other irAEs	Persistent Grade 2	Withhold	
 Based on severity of AE administer corticosteroids 	
 Ensure adequate evaluation to confirm etiology or exclude other causes
	Grade 3	Withhold or discontinue based on the event ^d		

irAEs	Toxicity Grade (CTCAE v5.0)	Action With Pembrolizumab	Corticosteroid and/or Other Therapies	Monitoring and Follow-up
	Recurrent Grade 3 or Grade 4	Permanently discontinue		

AE(s)=adverse event(s); ALT= alanine aminotransferase; AST=aspartate aminotransferase; CTCAE=Common Terminology Criteria for Adverse Events; DRESS=Drug Rash with Eosinophilia and Systemic Symptom; GI=gastrointestinal; IO=immuno-oncology; ir=immune related; IV=intravenous; SJS=Stevens-Johnson Syndrome; T1DM=type 1 diabetes mellitus; TEN=Toxic Epidermal Necrolysis; ULN=upper limit of normal.
 
Note: Non-irAE will be managed as appropriate, following clinical practice recommendations.
 
^a AST/ALT: >3.0 to 5.0 x ULN if baseline normal; >3.0 to 5.0 x baseline, if baseline abnormal; bilirubin:>1.5 to 3.0 x ULN if baseline normal; >1.5 to 3.0 x baseline if baseline abnormal
 
^b AST/ALT: >5.0 to 20.0 x ULN, if baseline normal; >5.0 to 20.0 x baseline, if baseline abnormal; bilirubin:>3.0 to 10.0 x ULN if baseline normal; >3.0 to 10.0 x baseline if baseline abnormal
 
^c AST/ALT: >20.0 x ULN, if baseline normal; >20.0 x baseline, if baseline abnormal; bilirubin: >10.0 x ULN if baseline normal; >10.0 x baseline if baseline abnormal
 
^d The decision to withhold or permanently discontinue pembrolizumab is at the discretion of the investigator or treating physician. If control achieved or ≤ Grade 2, pembrolizumab may be resumed.
 
^e Events that require discontinuation include, but are not limited to: encephalitis and other clinically important irAEs (eg, vasculitis and sclerosing cholangitis).
				

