- Thyroid function, T3, T4 and TSH should be monitored before initiation of, and periodically throughout treatment with lenvatinib. Hypothyroidism should be treated according to standard medical practice to maintain euthyroid state.
- Monitor patients for clinical symptoms or signs of cardiac dysfunction as dose interruptions, adjustments, or discontinuation may be necessary.
- Gastrointestinal toxicity should be actively managed in order to reduce the risk of development of renal impairment or renal failure. Dose interruptions, adjustments, or discontinuation may be necessary.

5.2.2.5 Dose Reductions/ Interruptions for non-immune related Adverse Events attributed to Lenvatinib

Table 5 Dose Modification Guidelines for Lenvatinib-related Adverse Events

Treatment-Related Toxicity ^{a,b}	Management	Dose Adjustment
Grade 1 or Tolerable Grade 2	Continue treatment	No change
Intolerable Grade 2 ^c or Grade 3 ^d		
First occurrence	Interrupt lenvatinib until resolved to Grade 0-1, or tolerable Grade 2	Reduce lenvatinib dose to 14 mg once a day (1-level reduction)
Second occurrence (same toxicity or new toxicity)	Interrupt lenvatinib until resolved to Grade 0-1, or tolerable Grade 2	Reduce lenvatinib dose to 10 mg once a day (1-level reduction)
Third occurrence (same toxicity or new toxicity)	Interrupt lenvatinib until resolved to Grade 0-1, or tolerable Grade 2	Reduce lenvatinib dose to 8 mg orally once a day (1-level reduction)
Fourth occurrence (same toxicity or new toxicity)	Interrupt lenvatinib	Discuss with PI
Grade 4 ^e : Discontinue Study Treatment		

Note: For grading see CTCAE version 5.0. Collect all AE grades (ie, decreasing and increasing CTCAE grade).

a An interruption of study treatment for more than 28 days will require Sponsor's approval before treatment can be resumed.

b Initiate optimal medical management for nausea, vomiting, hypertension, hypothyroidism and/or diarrhea prior to any lenvatinib interruption or dose reduction.

c Applicable only to Grade 2 toxicities judged by the participant and/or physician to be intolerable.

d For asymptomatic laboratory abnormalities, such as Grade ≥ 3 elevations of amylase and lipase that are not considered clinically relevant by the investigator, continuation of treatment should be discussed with PI.

e Excluding laboratory abnormalities judged to be non-life-threatening, in which case manage as Grade 3.

Abbreviations: AE = adverse event; CTCAE = Common Terminology Criteria for Adverse Events

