5.2.2.8 Management of Diarrhea

An anti-diarrheal agent should be recommended to the participant at the start of study treatment and participants should be instructed and educated to initiate anti-diarrheal treatment at the first onset of soft bowel movements. The choice of anti-diarrheal agent should be individualized to the participant's clinical circumstances and follow standard medical practice. If signs/symptoms of diarrhea persist despite optimal medical management, instructions contained in Table 5 should be

followed. If diarrhea does not improve, pembrolizumab-induced diarrhea should be considered and managed with corticosteroids as detailed in Table 3.

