5.2.2.9 Management of Hepatotoxicity

Liver function tests (alanine transaminase [ALT], aspartate transaminase [AST], bilirubin levels) should be conducted as detailed in the Study Flow Chart (Section 6.1) and as clinically indicated. If signs/symptoms indicating liver injury occur, instructions contained in Table 5 should be followed. Appropriate supportive care should be provided together with close monitoring. If hepatic failure occurs, the study drug must be discontinued. It might not be possible to determine whether LFT abnormalities are due to pembrolizumab or lenvatinib. Therefore, both drugs should be held and if no improvement is seen, corticosteroids should be initiated.

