5.2.2.11 Management of Posterior Reversible Encephalopathy Syndrome/Reversible

Encephalopathy Syndrome/ Reversible Posterior Leukoencephalopathy Syndrome

PRES/RPLS is a neurological disorder that can present with headache, seizure, lethargy, confusion, altered mental function, blindness, and other visual or neurological disturbances. Mild to severe hypertension may be present. MRI is necessary to confirm the diagnosis of PRES/RPLS. Appropriate measures should be taken to control BP. In participants with signs or symptoms of PRES/RPLS, instructions in Table 5 should be followed.

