5.2.2.14 Dose Modifications for Overlapping Toxicities

For overlapping toxicities where it is unclear if the event is related to one or both drugs, it is recommended to hold both drugs, and initiate management per Dose Modification Guidelines for Lenvatinib-Related Adverse Events. If toxicity does not improve within 1 to 2 days or worsens, management per Dose Modification Guidelines for Pembrolizumab-Related Adverse Events should be followed.

Participants who experience an unacceptable toxicity that is attributed to lenvatinib in the opinion of the investigator and the PI, may permanently discontinue lenvatinib, but may continue with pembrolizumab, upon resolution of toxicity to Grade 0 or 1 or baseline, until unacceptable toxicity or progression. Participants who discontinue pembrolizumab due to untoward toxicities may not continue on the trial receiving only lenvatinib.

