5.5.3 Rescue Medications & Supportive Care

Participants should receive appropriate supportive care measures as deemed necessary by the treating investigator. Suggested supportive care measures for the management of AEs with potential immunologic etiology are outlined along with the dose modification guidelines in Section 5.2.2, (Table 3). Where appropriate, these guidelines include the use of oral or IV treatment with corticosteroids, as well as additional anti-inflammatory agents if symptoms do not improve with administration of corticosteroids. Note that several courses of steroid tapering may be necessary as symptoms may worsen when the steroid dose is decreased. For each disorder, attempts should be made to rule out other causes such as metastatic disease or bacterial or viral infection, which might require additional supportive care. The treatment guidelines are intended to be applied when the Investigator determines the events to be related to pembrolizumab.

Note: If after the evaluation of the event, it is determined not to be related to pembrolizumab, the Investigator does not need to follow the treatment guidance. Refer to (Table 3) in Section 5.2.2 for guidelines regarding dose modification and supportive care.

It may be necessary to perform conditional procedures such as bronchoscopy, endoscopy, or skin photography as part of evaluation of the event.

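### For Grade 2 or higher diarrhea and liver-test events attributed to lenvatinib or of unclear cause, the protocol gives incompatible hold, steroid and stop instructions and states no order of precedence

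*Combined protocol and SAP*

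**What the plan says.** Section 5.2.2.1 deals with attribution first. An investigator may attribute an event to the combination, to pembrolizumab alone or to lenvatinib alone, but "for adverse events listed in Table 3, both interventions must be held according to the criteria in Table 3". Table 3 lists diarrhea/colitis and AST, ALT or bilirubin elevation. The next paragraph of the same section sets a condition: "if the AE is considered immune-related, both interventions should be held according to recommended dose modifications".

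Other sections direct the same events differently:

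- Section 5.2.2.4 sends lenvatinib toxicity that is not judged immune-related to Table 5. The lowest tier there, "Grade 1 or Tolerable Grade 2", means continuing without change.
- Section 5.2.2.8 (diarrhea) begins with an anti-diarrheal agent. Then: "If signs/symptoms of diarrhea persist despite optimal medical management, instructions contained in Table 5 should be" followed. Table 3 steroids come in only if the diarrhea does not improve.
- Section 5.2.2.9 (liver) first refers to Table 5. It then notes that the responsible drug may not be identifiable: "Therefore, both drugs should be held and if no improvement is seen, corticosteroids should be initiated".
- Section 5.2.2.14 (cause unclear between the drugs): "it is recommended to hold both drugs, and initiate management per Dose Modification Guidelines for Lenvatinib-Related Adverse Events". The pembrolizumab guideline takes over if the event worsens or has not improved in 1 to 2 days.
- Section 5.5.3: if the event is found not to be related to pembrolizumab, "the Investigator does not need to follow the treatment guidance", meaning Table 3.

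**The concern.** A site that meets one of these events has to choose a section. The choice decides whether both drugs stop, whether steroids start at once, and in some cases whether trial treatment ends for good. That is first a matter of patient safety: one reading risks steroids that are not needed, the other continued dosing through an immune event.

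It also bears on the data. The first brain MRI is at week 6 and confirmation is at week 12, so a hold or stop in that window changes exposure before the primary endpoint is read. Section 4.2.1 itself says that steroids could, in theory, hamper immune therapy. Section 5.7 provides for replacing participants who discontinue; on one reading of that sentence, the stop rule applied could affect who is counted. The trial has several sites, so different readings are foreseeable. The decision limits are small counts (4 responses in 27, and 7 in 29), so a change in a single patient can matter.

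**Working it through.** The plan states no figure to reproduce on this point. The check sets the instructions side by side for the same event and grade.

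| Event | Table 3, reached through 5.2.2.1 | Table 5 or the event section |
|---|---|---|
| Tolerable Grade 2 diarrhea | Withhold; the row also lists prednisone at 1 to 2 mg/kg | Table 5: continue, no change. 5.2.2.8: steroids only if no improvement |
| Recurrent Grade 3 diarrhea | Permanently discontinue | Table 5, second occurrence: interrupt until Grade 0-1 or tolerable Grade 2, then lenvatinib 10 mg |
| Grade 2 ALT | Withhold; steroids at 0.5 to 1 mg/kg | 5.2.2.9: hold both, steroids only if no improvement; it also cites Table 5, which says continue if tolerable |
| Grade 4 liver laboratory value, judged not life-threatening | Permanently discontinue | Table 5 footnote e: manage as Grade 3 (interrupt, then reduce) |

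**Does attribution settle it?**
1. Event attributed to lenvatinib and listed in Table 3: the first statement in 5.2.2.1 requires the Table 3 hold.
2. Same event, judged not immune-related: the next paragraph of 5.2.2.1 does not require the hold, 5.5.3 waives Table 3, and 5.2.2.4 sends it to Table 5.
3. Same event, cause unclear: 5.2.2.14 holds both drugs but applies the lenvatinib guideline first, whereas 5.2.2.1 applies Table 3 criteria from the start.

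No sentence ranks these instructions.

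**How far apart the paths are**
- Permanent discontinuation in Table 3 refers to pembrolizumab. Section 5.2.2.14 does not allow lenvatinib alone after pembrolizumab is stopped for toxicity, so the Table 3 path for recurrent Grade 3 diarrhea ends all trial treatment.
- Table 5 dose steps against the 20 mg start: 1 - 14/20 = 30% lower, 1 - 10/20 = 50% lower, 1 - 8/20 = 60% lower. Table 3 has no lenvatinib reduction step.
- Where Table 3 steroids are given, the taper begins at Grade 1 or below and lasts at least 4 weeks, and treatment may resume after it. That is at least 28 of the 42 days to the first scan (28/42 = 67%) for an event starting early in cycle 1. Infusions are 21 days apart, so at least one scheduled infusion falls within the hold. For tolerable Grade 2 diarrhea under Table 5 the hold is zero days.

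**How many patients**
- Section 4.2.2 reports any-grade treatment-related diarrhea in 48% of 21 melanoma patients on this combination.
- 0.48 x 27 = 13.0 melanoma patients; 0.48 x 29 = 13.9 RCC patients.
- Both figures include Grade 1, which Table 3 does not list for diarrhea and Table 5 leaves unchanged, so Grade 1 is not in conflict. The grade split is not given. The figures are ceilings for diarrhea at that rate, and the RCC one carries over a melanoma rate.

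**The case against.** The strongest reply is that the protocol does contain a sorting rule. Section 5.2.2.1 is headed for immune-related events, Table 3 is titled and columned for them, and a note under Table 3 leaves other events to clinical practice. Sections 5.2.2.4, 5.2.2.5 and 5.5.3 all fit that split. On this view the sentence in 5.2.2.1 overrides attribution to a drug, not the judgment of immune cause. Sections 5.2.2.8, 5.2.2.9 and 5.2.2.14 also give sequences and triggers, and 5.2.2.4 tells sites to read the event subsections before Table 5.

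Much of this stands as the likely intent. It does not remove the mandatory wording for every event listed in Table 3. The restart paragraph of 5.2.2.1 also expects events attributed to lenvatinib alone to be run against Table 3. The instruction in 5.2.2.4 orders the lenvatinib sections among themselves, but does not rank them against 5.2.2.1.

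Several stronger readings are tempting and are not supported:

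- **Steroids required in every case.** The sentence in 5.2.2.1 requires the hold. Steroids are listed in Table 3 but not expressly imposed for an event attributed to lenvatinib. For tolerable Grade 2 diarrhea, hold versus continue remains in conflict without them.
- **PRES.** Section 5.2.2.11 says "In participants with signs or symptoms of PRES/RPLS, instructions in Table 5 should be followed", and Table 3 does not name PRES. A conflict (interrupt and reduce versus permanent discontinuation at Grade 3) arises only if PRES is placed in the Table 3 row for neurological toxicities. Section 5.2.2.11 does call it a neurological disorder, so this is a secondary case that rests on inference.
- **Hypothyroidism.** Table 3 says continue, but for pembrolizumab; Table 5 acts on lenvatinib and requires medical management first. At Grade 3 these are not opposites. At most it needs clarifying.
- **A biased response rate.** Imaging follows calendar days and continues after stopping without progression, there is no comparator arm, and nothing in the documents allows an effect to be calculated.

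**Conclusion.** The concern holds for diarrhea and AST/ALT/bilirubin events of Grade 2 or above that are attributed to lenvatinib or are of unclear cause. For these the written instructions cannot all be followed, and patients with the same event can be managed differently. At the extremes, the difference is between no change and a hold of both drugs, or between a reduced lenvatinib dose and the end of all trial treatment.

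The conclusion rests on the text alone. A reader might infer that about 13 of 27 and 14 of 29 patients would fall under conflicting rules; the documents support these only as any-grade ceilings for diarrhea, the second by assumption. The share at Grade 2 or above, the share with liver events, and any shift in response rate or PFS are unknown. The case for correction is that the events are foreseeable, the instructions bear on safety and on treatment before the week-6 and week-12 scans, and the remedy is cheap. No view is taken on which clinical rule is right.

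**What to change.** State one order of precedence in Section 5.2.2 and bring 5.2.2.1, 5.2.2.8, 5.2.2.9, 5.2.2.14, 5.5.3 and Tables 3 and 5 into line with it. For diarrhea and for AST/ALT/bilirubin elevation, say which table governs at onset, what triggers a switch to the other, and what happens to each drug at each grade, including recurrent Grade 3 diarrhea and Grade 4 laboratory values. Settle whether the hold in 5.2.2.1 depends on the event being considered immune-related, and whether steroids go with it. In 5.2.2.11, say whether the Table 3 neurological row applies to PRES; a clarifying line on thyroid events would also help. The sponsor and clinical team decide which rule applies.

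The cost is amendment wording and a one-page memo to sites, with no added procedures. The drawback is that one of the discretionary paths now open to investigators would close.
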